	
Osteoarthritis is a 6-item scale validated to assess fear of movement in individuals with osteoarthritis
 
(v) Arthritis self-efficacy using the Arthritis-Self Efficacy Scale. This scale is scored from 1 to 10, with higher scores indicating greater self-efficacy, and was divided into the "pain" and "other symptoms" subscales
 
(vi) Physical and Mental Health using the PROMIS v.1.1 Global Health Short Form⁹. This scale is a 10-item survey that measures overall physical function, fatigue, pain, emotional distress, and social health in healthy and clinical adult populations¹⁰. We evaluated the measure divided into its two subscales: physical health and mental health¹¹.

--	--

Research Hypotheses

Hypothesis 1. A digital education and mindset intervention will significantly improve mindsets about the process of exercising and osteoarthritis among adults aged ≥ 45 years with knee osteoarthritis compared to an active comparison education intervention and no-intervention immediately post-intervention.

Hypothesis 2. A digital education and mindset intervention will significantly reduce knee pain and increase physical activity levels among adults aged ≥ 45 years with knee osteoarthritis compared to an active comparison education intervention and a no-intervention control group one-month post-intervention.

Hypothesis 3. A digital education and mindset intervention will significantly improve knee osteoarthritis knowledge and mindsets about activity adequacy and the body among adults aged ≥ 45 years with knee osteoarthritis compared to an active comparison education intervention and a no intervention control group immediately post-intervention.

Hypothesis 4. A digital education and mindset intervention will significantly improve knee pain and function, perceived need for surgery, symptom management, arthritis self-efficacy, fear of movement, physical health, mental health, among adults aged ≥ 45 years with knee osteoarthritis compared to an active-comparator education group and a no-intervention control group one-month post-intervention.

Key Personnel

Trial Coordinator

[name], [contact]
 Department of Bioengineering
 Stanford University, Stanford, California, USA

Statisticians

[name]
Department of Statistics
Stanford University, Stanford, California, USA

[name]
Department of Statistics
Stanford University, Stanford, California, USA

Trial Design

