The efficacy of the mindset intervention will be deemed successful if enhancements in either or both key outcomes, namely pain intensity (NRS) or physical activity levels (PASE), are observed. Anticipating modest effect sizes between the mindset and educational cohorts, we conducted a preliminary power analysis, similar to prior online education studies for knee osteoarthritis^{12,13}, using G*Power 3.1 with a presumed effect size of 0.3 (see below). This analysis involved comparing the mindset group against both the education and no-intervention groups, leading to four distinct comparisons. These assessments are planned to be executed at a 5% significance level, aiming for an 80% probability of discerning a noticeable improvement in delta. Based on Boswell et al.⁷, we estimated the standard deviations for PASE and pain at 70.28 and 1.67, respectively. A 26-point difference in PASE was selected as the target delta. While no clinically significant benchmarks for PASE has been established, the intervention's focus on promoting walking and moderate exercise led us to define this delta as the equivalent shift in walking and light exercise frequency from “seldom” (<1 hour per day) to “sometimes” (1-2 hours per day), as per the PASE scale, giving a goal of 26 points. This determination necessitates a sample size of 139 participants per group, totaling 417. To compensate for an anticipated 20% dropout rate, we plan to enroll 501 participants. This sample size is adequately powered to detect a clinically relevant difference of 2 points in NRS pain¹⁴.

A priori power analysis

[name]

11/29/2022

Let, y_i^b represents outcome at baseline and y_i^f represents outcome at follow-up for i^{th} person in treatment group, and \bar{y}^b and \bar{y}^f represents respective means. Similarly, x_i^b represents outcome at baseline and x_i^f represents outcome at follow-up for i^{th} person in control group, and \bar{x}^b and \bar{x}^f represents respective means.

Assumption: Let $x_i^f - x_i^b \sim \mathcal{N}(\Delta_1, \sigma^2)$ and $y_i^f - y_i^b \sim \mathcal{N}(\Delta_2, \sigma^2)$.

Let's say $\Delta = \Delta_2 - \Delta_1$, we want to test the hypothesis

$$H_0 : \Delta = 0$$

$$\text{v/s } H_1 : \Delta > 0$$

Under H_0 , $T = (\bar{y}^f - \bar{y}^b) - (\bar{x}^f - \bar{x}^b) \sim \mathcal{N}(0, 2\sigma^2/n)$. We reject H_0 if $\frac{T}{\sqrt{2\sigma^2/n}} > z_{1-\alpha}$. We want n so that power at Δ is $1 - \beta$, i.e.,

[figure not shown]

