$$P_{\Delta} \left(\frac{T}{\sqrt{2\sigma^2/n}} > z_{1-\alpha} \right) \geq 1 - \beta$$

which is equivalent to

$$n \geq \frac{2\sigma^2(z_{1-\alpha} + z_{1-\beta})^2}{\Delta^2}$$

[figure not shown]
For our analysis, we choose $\alpha = 0.05$, and try four different values of β , 0.05, 0.10, 0.15, and 0.20. We estimate σ from pilot data.

Outcome variable, PASE

[figure not shown]
[figure not shown]

sigma = 70.27939

A priori sample size analysis for outcome variable, PASE

[figure not shown]

Pain Scores

sigma = 1.670426

A priori sample size analysis for outcome variable, pain

Recruitment

Participants will be recruited through paid online and social media advertising and local flyer postings.

Allocation

We will use the randomizer function in Qualtrics to randomize participants into one of three groups (1:1:1): the Mindset Group, the Education Group (active comparison), or the No-Intervention Group (control).

Blinding (Masking)

During the informed consent process, participants will be informed that the purpose of the study is to understand the effect of a new online osteoarthritis program and that they will be randomized to either a no-intervention group or one of two different sets of videos and reflective questions. Participants will be aware of whether they are randomized to an online program; however, the differences in content between the two programs and the hypotheses of the study will not be revealed. The biostatistician performing the data analysis will be blinded to the group labels.

Data Collection, Management, and Access

All data will be collected through the Qualtrics online survey software. Qualtrics encrypts all transmitted data using Transport Layer Security and hosts data on data centers that are independently audited using the industry standard SSAE-18 method. Stanford University has a Qualtrics license for research use, and data obtained from the Qualtrics platform can only be accessed through a secure login. Data will be exported to Microsoft Excel and securely stored for use by the research team. Only after de-identification may the data be shared outside of the research team.

Missing Data

Participants who did not complete a survey entirely were removed from the study and not sent the follow-up survey. Each question of each survey was “force response,” meaning that if a participant completed the survey, no answers would be missing from the response. Thus, no methods for missing data were implemented.

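### The 139 per group does not follow from 26 PASE points at the stated 5% level (that gives 91), and at the 0.0125 threshold used in the analysis the stated 80% power holds only for 26 points tested one-sided, which the plan never declares

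*Combined protocol and SAP*

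**What the plan says.** The Sample Size section describes a G*Power analysis "with a presumed effect size of 0.3 (see below"), comparing the mindset group with both other groups, "leading to four distinct comparisons". On level and power it says: "These assessments are planned to be executed at a 5% significance level, aiming for an 80% probability of discerning a noticeable improvement in delta". It then takes SDs of 70.28 (PASE) and 1.67 (pain) and adds: "A 26-point difference in PASE was selected as the target delta". After justifying the 26 points it concludes: "This determination necessitates a sample size of 139 participants per group, totaling 417". The intervention "will be deemed successful if enhancements in either or both key outcomes" are seen.

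The a priori power analysis tests a zero difference in mean change against a positive one, so it is one-sided. It gives a normal-theory formula for n and says: "we choose $\alpha = 0.05$, and try four different values of β , 0.05, 0.10, 0.15, and 0.20".

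Statistical Methods specifies pooled-variance t-tests of change and a Bonferroni correction over the four comparisons, with a threshold of 0.0125. It does not say whether the tests are one- or two-sided. Hypothesis 2 predicts that the intervention "will significantly reduce knee pain and increase physical activity levels", which gives an expected direction but no rejection region.

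**The concern.** The sample-size text and the derivation both work at 5%, while the analysis tests at 0.0125. The text also carries two effect sizes, 0.3 and 26/70.28 = 0.37, and does not reconcile them. The paragraph ties 139 to the 26 points, yet that target at the printed alpha does not give 139.

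At stake is what the 80% refers to. A reader will take it as the chance of detecting the target in the analysis as planned. Whether that is so depends on which effect size is meant and on the sidedness of the 0.0125 test, and the plan fixes neither. If sidedness is left open until the data are in, it can also decide a primary result.

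**Working it through.** **Inputs.** PASE SD σ = 70.27939 (70.28 in Sample Size); target Δ = 26, so d = 26/70.28 = 0.37; presumed effect size 0.3; power 80%; alpha 0.05 (Sample Size and derivation); threshold 0.0125 = 0.05/4 (Statistical Methods); stated n = 139 per group.

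**Step 1: the target and alpha as printed.** The plan's formula is n = 2σ²(z₁₋α + z₁₋β)²/Δ². Here 2σ²/Δ² = 2 × 70.27939²/26² = 14.61.
- α = 0.05, β = 0.20: 14.61 × (1.645 + 0.842)² = 90.3, so 91.
- α = 0.05 with the other listed β values of 0.15, 0.10 and 0.05: 105.1, 125.1 and 158.1.

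None of these is 139.

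**Step 2: what does give 139.**
- *Route A, effect size 0.3 at one-sided 0.05.* With the noncentral t (df = 2n − 2, noncentrality d√(n/2)), power is 79.98% at n = 138 and 80.2% at n = 139, so n = 139. The normal formula gives 2 × (1.645 + 0.842)²/0.3² = 137.4, so 138.
- *Route B, 26 points at one-sided 0.0125.* The normal formula gives 14.61 × (2.241 + 0.842)² = 138.9, so 139. Two-sided 0.025 is numerically the same. The noncentral t gives 141.

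Route A uses inputs that are all printed but makes no allowance for four comparisons. Route B keeps the 26-point target but needs an alpha that neither the Sample Size text nor the derivation prints.

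**Step 3: power of the analysis that will be run.** Noncentral t, 139 per group, df = 276, level 0.0125, per comparison. Critical t is 2.254 one-sided and 2.514 two-sided. Noncentrality is 0.37 × √69.5 = 3.08 for 26 points and 0.3 × √69.5 = 2.50 for d = 0.3.

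| Effect | One-sided 0.0125 | Two-sided 0.0125 |
|---|---|---|
| 26 PASE points (d = 0.37) | 79.6% | 71.5% |
| d = 0.3 (21.1 PASE points) | 59.8% | 49.6% |
| PASE difference detectable with 80% power | 26.1 points | 28.3 points |

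For 26 points at two-sided 0.0125 the plan's formula would ask for 14.61 × (2.498 + 0.842)² = 163 per group.

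**Step 4: can sidedness decide a result?** The standard error is 70.28 × √(2/139) = 8.43 points. The critical differences are 2.254 × 8.43 = 19.0 points one-sided and 2.514 × 8.43 = 21.2 two-sided. An observed difference between them passes one test and fails the other, and 0.3 SD (21.1 points) lies in that window.

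**Step 5: the pain statement.** For 2 NRS points, d = 2/1.67 = 1.20, and power exceeds 99.9% even two-sided.

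**The case against.** The strongest reply is that the plan does contain a consistent calculation. It names the tool, the effect size (0.3), the level (5%) and the power (80%), its derivation is one-sided, and these inputs give exactly 139 by the noncentral t. On that view the 26 points are a clinical gloss and the printed alpha is right.

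This stands as far as it goes. A reader might infer from the 91 that 139 must have been computed at one-sided 0.0125, that the alpha in the derivation is therefore a misprint, or that n cannot be reproduced from alpha 0.05. The documents support none of these: Route A reproduces n with the printed alpha. Nor is it true that 80% never applies to 0.3, since at one-sided 0.05 it does.

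The reply does not clear the plan, though. If Route A was used, n ignores the Bonferroni threshold, and power for 0.3 at the tested level is about 60% or 50%. If Route B was used, the printed alpha is wrong and the 80% depends on an undeclared one-sided test. The missing plots may show which route was taken, but they would not change the alpha printed in the text or put a direction into Statistical Methods.

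It can also be said that success on either outcome is enough, so the chance of some success exceeds the per-comparison figures. That is correct. As an illustration, suppose d = 0.3 for both PASE and pain against one comparator, with a correlation between 1 and 0 (an assumption; the plan gives none). The chance that at least one passes is then 60% to 84% one-sided, or 50% to 75% two-sided, where 84% is 1 − (1 − 0.598)². The plan does not present its 80% as this quantity.

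**Conclusion.** The point holds as a failure of reconciliation. The sample size as written (26 points, 5%, 80%) gives 91 per group, not 139. Two different calculations give 139, and the available text does not settle which was used. At the 0.0125 threshold, per-comparison power with 139 per group is about 80% one-sided or 72% two-sided for 26 points, and about 60% or 50% for d = 0.3. The stated 80% therefore describes the planned analysis only for 26 points tested one-sided.

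These figures assume 139 analysed per group, the plan's SD, equal variances and normally distributed changes. They do not show that the trial is too small: the 2-point NRS claim is unaffected, and 26 points keeps about 72% power even two-sided. This should be fixed, but it gives no reason to change enrolment.

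**What to change.** Leave enrolment unchanged and revise the text:

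1. State which effect size, alpha and sidedness produced 139, and make Sample Size and the a priori power analysis agree with that calculation. The sponsor should establish this from its records; neither route should be presumed.
2. State that 5% is the family-wise level over the four comparisons and 0.0125 the per-test level.
3. Declare in Statistical Methods whether each 0.0125 test is one- or two-sided. If one-sided, give the direction per outcome: an increase in PASE and a decrease in NRS pain. The derivation's alternative of a positive difference cannot serve both unless pain is reverse-signed.
4. Restate power at 0.0125 for both 26 points and d = 0.3, labelled as per comparison. Two-sided: about 72% for 26 points (80% for about 28 points) and about 50% for d = 0.3. One-sided: about 80% and 60%.

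The sentence on 2 NRS points can stay. The cost is wording only, with no added participants. The drawback is that the stated power becomes less favourable for d = 0.3, and also for 26 points if two-sided tests are declared.

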Source(s) of monetary or material support	
The Wu Tsai Human Performance Alliance at Stanford University and the Joe and Clara Tsai Foundation. The Stanford Catalyst for Collaborative Solutions; the Mobilize Center, which is supported by the National Institute of Biomedical Imaging and Bioengineering (NIBIB) and the Eunice Kennedy Shriver National Institute Of Child Health & Human Development (NICHD) of the National Institutes of Health (NIH) under Grant P41EB027060; and the Center for Reliable Sensor Technology-Based Outcomes for Rehabilitation (RESTORE), which is supported by the Eunice Kennedy Shriver National Institute Of Child Health & Human Development (NICHD) and the National Institute Of Neurological Disorders And Stroke (NINDS) of the National Institutes of Health (NIH) under Grant No. P2CHD101913.

Primary sponsor	Stanford University
Contact for public queries	[name] Stanford University [contact]
Contact for scientific queries	[name] Stanford University [contact]
Title	A Digital Mindset Intervention to Improve Pain and Exercise Participation in Individuals With Knee Osteoarthritis: A Randomized, Parallel-group Study
Countries of recruitment	USA
Health condition(s) or problem(s) studied	Knee osteoarthritis
Study type	Interventional Allocation: randomized Intervention model: parallel assignment Masking: Subjects not blind; outcomes assessor blind Primary purpose: Supportive Care
Date of first enrolment	April 2023
Target sample size	501

Choice of comparator

Education and exercise are recommended as first-line treatment for osteoarthritis, but often, “treatment as usual” is pain medication and, eventually, surgery. If patients want information about osteoarthritis, sometimes they are given a pamphlet about osteoarthritis by their doctor. Otherwise, they are left to research osteoarthritis on their own. Our comparator is education videos about osteoarthritis that one would typically find on the internet. While accurate, this information does not typically (or intentionally) target mindset and, as shown in the low physical activity levels and adherence to exercise, does not successfully support behavior change. As this does not put

participants at risk, we expect that it will neither improve nor worsen their physical or psychological states.

Supplement 1 Table 2. Study Objectives

Primary Objectives	

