We will randomize 505 individuals aged ≥ 45 years with knee osteoarthritis into one of three groups with 1:1:1 group allocation: the Mindset Group (participants receive a digital mindset intervention to improve mindsets about osteoarthritis and exercise), the Education Group (Participants receive a series of osteoarthritis education videos and reflective questions that matches the digital mindset intervention in duration and attention), or the No-Intervention Group (participants take the same surveys as the other groups at the same time points, but do not receive any additional content). Participants will complete an initial baseline survey and be randomized one week later. Those randomized to the Mindset and Education Groups will have one week to complete the self-paced online programs. All groups complete osteoarthritis knowledge and mindset surveys at this timepoint. One-month later, participants will receive a follow-up questionnaire.

Study Setting

The study will be conducted entirely online.

Eligibility Criteria

Inclusion Criteria:

- Over 45 years of age
- Self-reported doctor's diagnosis of knee osteoarthritis OR meets the National Institute for Health and Care Excellence osteoarthritis clinical criteria (activity-related knee pain and no knee morning stiffness lasting ≥ 30 minutes)
- Knee pain for at least 3 months
- Ability to walk unaided
- Can read and write in English
- Consistent internet access
- Willingness and ability to comply with the study requirements

Exclusion criteria:

- Past total knee arthroplasty or scheduled surgical procedure on any back or

- lower limb with osteoarthritis within the next 12 months
- Recent serious injury (within the past 2 months) on the knee(s) with osteoarthritis
- Any condition making it unsafe to participate in physical activity
- Intra-articular therapy within the past 6 months (e.g. injections such as corticosteroids and hyaluronic acid)
- Participates in physical exercise for 30 minutes or more 5 days per week

Interventions

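### The 20% dropout allowance was added as 417 × 1.2 instead of 417 / 0.8, so 501 enrolled leaves about 134 per group, not the required 139

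*Combined protocol and SAP*

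**What the plan says.** The Sample Size section sets the analysable number: "This determination necessitates a sample size of 139 participants per group, totaling 417". It then makes the allowance for losses: "To compensate for an anticipated 20% dropout rate, we plan to enroll 501 participants". The study meta-data table (Supplement 1 Table 1) repeats the enrolment figure: "Target sample size 501". Trial Design gives another: "We will randomize 505 individuals". Allocation is 1:1:1 in both Trial Design and Allocation.

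The Missing Data section says that anyone who did not finish a survey was taken out of the study and sent no further survey, and that no missing-data method was used. The primary analysis (Statistical Methods) is a two-sample t-test on change scores, so a participant without the one-month survey contributes nothing to the PASE and pain comparisons.

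**The concern.** A dropout rate is a fraction of the people enrolled. To end with N completers when a proportion d is lost, enrolment must be N / (1 − d). Multiplying N by (1 + d) gives too few, because the loss is then taken from the larger number. The figure 501 looks like the second calculation.

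If so, the enrolment does not deliver the 139 per group that the plan says it needs, under the plan's own dropout assumption. PASE is the outcome that set the sample size, and there is almost no slack in 139. The plan also gives two enrolment targets, 501 and 505, so a reader cannot tell which one governs.

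**Working it through.** **Inputs**

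- Target difference 26 points (Sample Size: "A 26-point difference in PASE was selected as the target delta").
- SD of change (A priori power analysis: "sigma = 70.27939").
- Power 80% (Sample Size).
- One-sided alternative (A priori power analysis).
- Per-comparison threshold 0.05 / 4 = 0.0125 (Statistical Methods, Bonferroni correction).
- Dropout 20%; enrolment 501 (Sample Size, Table 1) or 505 (Trial Design).

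**Step 1: reproduce 139.** The plan's formula is n ≥ 2σ²(z₁₋α + z₁₋β)² / Δ².

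- With one-sided α = 0.0125, z₁₋α = 2.2414; with 80% power, z₁₋β = 0.8416.
- n = 2 × 70.27939² × (3.0830)² / 26² = 138.9, rounded up to 139. Three groups give 417.
- Other readings with Δ = 26 do not give 139: one-sided 0.05 gives 91, two-sided 0.05 gives 115, two-sided 0.0125 gives 163.

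So 139 is the completer requirement at one-sided 0.0125, with no allowance for losses built in.

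**Step 2: reproduce 501.**

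- 417 × 1.20 = 500.4, rounded up to 501.
- By group: 139 × 1.20 = 166.8, rounded up to 167; 3 × 167 = 501.

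Both routes give 501 exactly.

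**Step 3: the allowance that keeps 417.**

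- 417 / (1 − 0.20) = 521.25, rounded up to 522, or 174 per group. Check: 174 × 0.80 = 139.2.
- 522 − 501 = 21 more participants.

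**Step 4: what the stated enrolments deliver.**

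| Enrolled | Left after 20% loss | Per group | Short of 417 | Dropout that still leaves 417 |
|---|---|---|---|---|
| 501 | 400.8 | 133.6 | 16.2 | 1 − 417/501 = 16.8% |
| 505 | 404.0 | 134.7 | 13.0 | 1 − 417/505 = 17.4% |
| 522 | 417.6 | 139.2 | none | 1 − 417/522 = 20.1% |

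**Step 5: effect on power for 26 PASE points**, as Φ(Δ / (σ√(2/n)) − z₁₋α), one-sided 0.0125:

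- n = 139: Φ(3.084 − 2.241) = 80.0%
- n = 134.67 (505 enrolled): 78.7%
- n = 133.6 (501 enrolled): Φ(3.024 − 2.241) = 78.3%
- n = 133: 78.1%

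The noncentral t distribution gives 79.6% at 139 and 77.7% at 133, a fall of the same size. If the final tests are two-sided at 0.0125, the noncentral-t figures are 71.5% and 69.2%. Most of that gap from 80% is already there at 139 and comes from sidedness; the dropout arithmetic adds about 2 points.

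For a 2-point pain difference with SD 1.670426, power at 133 per group is above 99.9%, even two-sided at 0.0125.

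**The case against.** The best defence is that the slip hardly matters. It costs 1.7 points of PASE power on the plan's own formula (80.0% to 78.3%). Pain is unaffected, and the plan counts the trial a success if either outcome improves. All of this is correct, and it limits how much weight the point should carry. It does not make the sentence true: 501 does not compensate for 20% dropout.

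A second argument is that the power derivation itself states α = 0.05, not 0.0125. At 0.05, 133 per group would give 91.5% power one-sided or 85.5% two-sided, above the target. But at 0.05 the required number would be 91 or 115 per group, not 139. The shortfall against the stated 139 remains on any reading. The power figures above rest on 0.0125, which the power section does not state but which is the value that reproduces 139 with a 26-point difference.

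A third concerns 505. Trial Design places randomisation one week after the baseline survey, and the documents do not say from which point dropout is counted. If some of the 20% is lost before randomisation, 505 randomised would lose less than 20% afterwards and could reach 417 if later losses stay at or below 17.4%. That stands as a caveat on the 505 row. It does not help 501, which the plan describes as the number enrolled.

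**Conclusion.** The concern holds. The figure 501 is the requirement plus 20%, and under the plan's own dropout rate it leaves about 401 completers (133 to 134 per group) instead of 417 (139 per group). It tolerates 16.8% dropout, not 20%. The figure 505 conflicts with it and also falls short if 20% of those 505 are lost.

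The size is modest: about 16 completers, and a little under 2 points of power for PASE. This assumes that dropout is a proportion of those enrolled, falls evenly across the groups, and removes participants from the analysis, as the Missing Data section implies. The power figures further assume one-sided 0.0125 and an SD of 70.28. Whether the final tests are one- or two-sided matters more for power than this slip does, and is a separate question.

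**What to change.** Enrolment need not change. Amend the Sample Size section in one of two ways:

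- State that 501 enrolled with 20% dropout gives about 401 completers, 133 to 134 per group, and restate the power at that number: about 78% for 26 PASE points at one-sided 0.0125, with the threshold and sidedness written beside it.
- Or state that 417 completers requires dropout of no more than 16.8% of 501 (84 participants).

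Use one enrolment figure in Table 1, Trial Design and Sample Size, and say whether it counts people enrolled or randomised and from which point dropout is measured. If 505 is kept, the matching figures are 404 completers (134 to 135 per group), 17.4% tolerated dropout and 78.7% power.

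The cost is a few sentences and a slightly less favourable stated power. Keeping both the 20% allowance and 139 per group would instead need 522 enrolled, 21 more than 501.
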